2.4. Statistical Analyses

Given that this is a FTiH study, statistical analyses planned will be mainly descriptive in nature involving frequencies and percentages for categorical variables and number of subjects (n), mean, standard deviation, median, minimum and maximum for continuous variables.

Where appropriate (for e.g., evaluation of dose proportionality, drug accumulation, food effect) statistical modelling will be performed and point estimates with 90% confidence intervals (CIs) will be constructed.

3. PLANNED ANALYSES

3.1. Interim Analyses

No formal interim analyses (IA) are planned for this study. However, regular dose escalation meetings, an informal IA and safety review meetings are planned to be performed at different time points described below.

- Dose escalation meetings are planned to review the safety, tolerability, and PK data prior to:
 - each dose escalation in Part A (single dose) – Cohorts 1 and 2,
 - initiation of the food effect Cohort 3, and
 - each dose escalation in Part B (repeat dose) – prior to initiation of Cohorts 5 and 6.
- An informal IA to review the safety, tolerability, and PK data from Part A is planned prior to:
 - progression to Part B.
- Additional instream safety review meetings including all safety and tolerability data only are planned prior to:
 - progression to Cohort 2 in Part A
 - progression to Period 2 in the food effect Cohort 3.

There will not be a formal database freeze performed for this informal IA. Data included for these analyses will be as complete and clean as possible based on continuous data review and monitoring activities.

The final study analysis post- database freeze will include all data captured in the study database.

3.1.1.1. Dose escalation meetings

Statistical displays will not be produced by Biostatistics for the dose escalation meetings. During the meeting, safety data (presented by the CUC Principal Investigator or delegate) and PK data (presented by Study Pharmacokineticist or delegate) will be reviewed by the committee.

The meeting will discuss blinded data in an open forum with the GSK Study team members and Principal Investigator (or their delegate) in attendance. If required, the data may be reviewed in an unblinded fashion by the unblinded members including the SMG (formally GCSP) Safety representative and Study Pharmacokineticist.

The decision to proceed to the next dose level of GSK3186899 will be made at a DEC meeting based on:

- all available safety and tolerability data from individuals (including AEs, laboratory safety tests, telemetry, ECGs and vital signs) from a minimum of 48 hours post-dose (10 days for repeat dose) from a minimum of 4 or more participants who have received GSK3186899 at the current dose level

- all available safety and tolerability data accumulated from preceding single/repeat dose levels and available PK data from current (minimum of 4 or more participants) and preceding single/repeat dose levels.

Further details of the DEC membership, data to be reviewed and stopping criteria are outlined in the DEC charter.

3.1.1.2. Informal interim analysis

An informal interim analysis (IA) after completion of Part A will be conducted prior to initiation of Part B. This analysis will support the decision to progress, or, not progress to Part B and will consist of the following statistical displays on blinded safety and blinded PK data. Safety tables will therefore be presented by period rather than treatment to maintain the blind of the study.

Table 1: Planned Statistical Displays for the Interim analysis

Sl. No.	Population	IDS / Example Shell	Title	Responsible function
1	Safety	ES1A	Summary of Participant Disposition for the Participant Conclusion Record – Part A (Cohort 1 and Cohort 2 only)	Biostatistics
2	Safety	ES3	Listing of Reasons for Study Withdrawal – Part A (Cohort 1 and Cohort 2 only)	Biostatistics
3	Safety	SD3	Listing of Reasons for Study Treatment Discontinuation – Part A (Cohort 1 and Cohort 2 only)	Biostatistics
4	Safety	DM3	Summary of Demographic Characteristics – Part A (Cohort 1 and Cohort 2 only)	Biostatistics
5	Safety	DM4	Listing of Demographic Characteristics - Part A (Cohort 1 and Cohort 2 only)	Biostatistics
6	Safety	EX1	Summary of Exposure to Study Treatment - Part A (Cohort 1 and Cohort 2 only)	Biostatistics
7	Safety	EX4	Listing of Exposure Data – Part A (Cohort 1 and Cohort 2 only)	Biostatistics
8	Safety	AE1CP	Summary of All Adverse Events by System Organ Class and Preferred Term - Part A (Cohort 1 and Cohort 2 only)	Biostatistics
9	Safety	AE9	Listing of All Adverse Events - Part A (Cohort 1 and Cohort 2 only)	Biostatistics
10	Safety	EG4	Listing of All ECG Values for Subjects with Any Value of Potential Clinical Importance - Part A (Cohort 1 and Cohort 2 only)	Biostatistics
11	Safety	EG6	Listing of All ECG Findings for Subjects with an Abnormal Finding - Part A (Cohort 1 and Cohort 2 only)	Biostatistics
12	Safety	LB6	Listing of All Laboratory Data for Participants with Any Value of Potential Clinical	Biostatistics

			Importance – Part A (Cohort 1 and Cohort 2 only)	
13	Safety	UR2B	Listing of All Urinalysis Data for Subjects with Any Value of Potential Clinical Importance - Part A (Cohort 1 and Cohort 2 only)	Biostatistics
14	Safety	VS5	Listing of All Vital Signs for Subjects with values Potential Clinical Importance - Part A (Cohort 1 and Cohort 2 only)	Biostatistics
15	Safety	EG6 (to be modified for telemetry data)	Listing of Telemetry findings - Part A (Cohort 1 and Cohort 2 only)	Biostatistics
16	Safety	DV2	Listing of Important Protocol Deviations – Part A (Cohort 1 and Cohort 2 only)	Biostatistics
17	PK	Non standard shell	Summary of Untransformed Derived GSK3186899 Plasma Pharmacokinetic Parameters by dose and fed status - Part A (All Cohorts)	CPMS
18	PK	Non standard shell	Summary of the ratio of fed versus fasted on AUC($0-\infty$) and Cmax – Part A Cohort 3	CPMS
19	PK	Non standard shell	Geo Mean (+ SD) GSK3186899 Plasma Concentration-Time Plot (Linear and Semi-Log) – Part A (Cohort 1 and Cohort 2 only)	CPMS
20	PK	Non standard shell	Box Plot of AUC($0-\infty$) and Cmax versus dose (Linear) – Part A (Cohort 1 and Cohort 2 only)	CPMS
21	PK	Non standard shell	Box Plot of dose normalised AUC($0-\infty$) and Cmax versus dose (Linear) – Part A (Cohort 1 and Cohort 2 only)	CPMS
22	PK	Non standard shell	Geo Mean (+ SD) GSK3186899 Plasma Concentration-Time Plot (Linear and Semi-Log) grouped by fed and fasted status – Part A Cohort 3	CPMS
23	PK	Non standard shell	Box Plot of AUC ($0-\infty$) and Cmax (Linear) grouped by fed and fasted status – Part A Cohort 3	CPMS
24	PK	Non standard shell	Listing of GSK3186899 Plasma Pharmacokinetic Concentrations (\log_e -transformed) -Time Data by dose - Part A (All Cohorts)	CPMS

The PK related displays will be prepared by/under the auspices of the CPMS function and the safety related displays will be prepared by/under the auspices of the Biostatistics function.

The safety related IA displays will include data from Cohort 1 and Cohort 2 only. This is because all the doses will be investigated for safety and tolerability during these two cohorts and Cohort 3 will provide further information on the fed or fasted regimen to be applied in the Part B, for multiple ascending doses.

The actual treatment information will not be presented in any displays. Aggregated data will be reported in the tables of safety endpoints. The PK data will be presented without subject IDs. Blinded listings of safety and PK data will be provided.

A blinded dry run will be performed prior to the informal IA. The dry run displays will be reviewed by the study team including SMG Pharma Safety representative.

If required and/or requested by the DEC, an independent statistician and programmer(s) may be deployed to create unblinded displays.

However, a support pharmacokineticist in GSK will have access to extract scrambled PK data from SMS2000 to PKHARP and transfer the data via secured email to the Study pharmacokineticist (in PAREXEL International) for their reviews and analyses during study.

In case, there are any serious adverse events requiring further investigation, the unblinded SMG Pharma Safety representative and unblinded Study Pharmacokineticist can support further investigation.

3.1.1.3. Safety review meetings

The decision to proceed from Cohort 1 Period 4 to Cohort 2 Period 1 and similarly progress from Cohort 3 Period 1 (DLX) to Cohort 3 Period 2 (DLX-FD) will be made by the Principal Investigator and Medical Monitor based on all available safety and tolerability data from a minimum of 48 hours post-dose from a minimum of 4 or more participants who have received GSK3186899 at the current dose level. Individual safety data (AEs, laboratory safety tests, telemetry, ECGs and vital signs) will also be reviewed. PK data will not be included in these reviews.

The study team will remain blinded until the database freeze, except for the unblinded site Pharmacist, unblinded study Pharmacokineticist and SMG Pharma Safety representative.

3.2. Final Analyses

The final planned analyses will be performed after the completion of the following sequential steps:

1. All participants have completed the study as defined in the protocol.
2. All required database cleaning activities have been completed and final database release (DBR) and database freeze (DBF) have been declared by Data Management.
3. All criteria for unblinding the randomization codes have been met.
4. Randomization codes have been distributed according to RandAll NG procedures.

A final blinded dry run will be performed prior to the database lock for review by the study team.

4. ANALYSIS POPULATIONS

For purposes of analysis, the following populations are defined:

Population	Description	Analyses Evaluated
Screened	
 All participants who were screened for eligibility 	
 Screen Failure
Enrolled	
 All participants who passed screening and entered the study. Included are: Randomized Participants 
Note: screening failures (who never passed screening even if rescreened) and participants screened but never enrolled into the study (Reserve, Not Used) are excluded from the Enrolled population as they did not enter the study.
	
 Study Population
Safety	
 All randomized participants who received at least one dose of study treatment. This population will be based on the treatment the subject actually received. 
Note: Participants who were not randomized but received at least one dose of study treatment should be listed.
	
 Study Population Safety
PK	
 All participants in the Safety population who had at least 1 non-missing PK assessment* (Non-quantifiable [NQ] values will be considered as non-missing values). 	
 PK

Refer to **Error! Reference source not found.**: List of Data Displays which details the population used for each display.

* PK assessments refer to the plasma concentrations and not the PK parameters.

4.1. Protocol Deviations

Important protocol deviations (PDs), including deviations related to study inclusion/exclusion criteria, conduct of the trial, patient management or patient assessment) will be summarised and listed.

Protocol deviations will be tracked by the study team throughout the conduct of the study in accordance with the Protocol Deviation Management Plan [Version 1.0 dated 10 April 2019 or later].

Exclusion from the analysis sets due to a deviation will be determined programmatically using the criteria described in the table of Analysis populations above. These deviations will not be included in the SDTM dataset but will be programmed in the protocol deviation analysis (ADaM) dataset. This dataset will be the basis for the summaries and listings of protocol deviations.

Data will be reviewed prior to unblinding and freezing the database to ensure all important deviations and deviations which may lead to exclusion from the analysis are captured and categorised.

A separate summary and listing of all inclusion/exclusion criteria deviations will also be provided. This summary will be based on data as recorded on the inclusion/exclusion page of the eCRF.

5. CONSIDERATIONS FOR DATA ANALYSES AND DATA HANDLING CONVENTIONS

5.1. Study Treatment & Sub-group Display Descriptors

Treatment Group Descriptions			
RandAll NG		Data Displays for Reporting	
Code	Description	Description	Order in TLF
PART A			
P1 / P2	Placebo cohort 1 / Placebo cohort 2	Placebo Part A	1
D1	GSK3186899 Dose Level 1	GSK 30 mg	2
D2	GSK3186899 Dose Level 2	GSK 60 mg	3
D3	GSK3186899 Dose Level 3	GSK 120 mg	4
D4	GSK3186899 Dose Level 4	GSK 300 mg	5
D5	GSK3186899 Dose Level 5	GSK 600 mg	6
D6	GSK3186899 Dose Level 6	GSK 800 mg	7
D7	GSK3186899 Dose Level 7 (this dose was not investigated)	GSK X.X mg	8
DX-FA	GSK3186899 Dose Level X fasted	GSK X.X mg fasted	9
DX-FE	GSK3186899 Dose Level X fed	GSK X.X mg fed	10
PART B			
P4/ P5/ P6	Placebo cohort 4/ Placebo cohort 5/ Placebo cohort 6	Placebo Part B	1
R1	GSK3186899 Repeat Dose Level 1	GSK X.X mg BID	2
R2	GSK3186899 Repeat Dose Level 2	GSK X.X mg BID	3
R3	GSK3186899 Repeat Dose Level 3	GSK X.X mg BID	4

Note: Doses levels 1 to 6 were known at the time of RAP finalisation. The later doses were unknown, but will be known and detailed in the final study reporting.

For Part A, this order of the treatments will be considered for displays including all treatment groups from Cohorts 1, 2 and 3. However, for displays by Cohorts, only relevant treatment groups will be presented in the same ascending order mentioned above.

Treatment comparisons will be displayed using the descriptors as specified below:

- In general, comparison between 2 doses: GSK X.X mg vs GSK X.X mg
- In Cohort 3 (same dose different food regimen): GSK X.X mg - fed vs fasted.

5.2. Baseline Definitions

Baseline is defined as the last non-missing pre-dose assessment in each cohort. In general, assessments on Study day 1 taken prior to first dose are used as baseline. In some unlikely situations described below, the baseline will be defined as:

- when there are multiple assessments captured on Day 1, but the time of the first assessments is missing, then this first recorded assessment will be considered as the baseline
- when only one assessment is captured on Day 1 with time of assessment as missing, then conservatively the last available assessment from Day -1 or prior will be defined as the baseline
- when there are no assessments collected at Day 1, the last available data from either Day -1/ Day -2 or screening (as schedule of assessment in each Part/Cohort permits) will be defined as baseline
- when pre-dose data is completely missing for a subject, then no derivation will be performed, and the baseline will be set to missing

In Part A, for each period within a cohort, the period baseline is defined in a similar manner, by considering the last available non-missing pre-dose assessment in that period.

For some ECG and Vital Signs parameters, the pre-dose data is captured as triplicate. In these cases, the baseline will be defined as the mean of the assessments.

In addition, for some PK endpoint analyses, the adjusted baselines may be considered, if the pre-dose PK concentration value in a period is observed to be greater than 5% of the previous dose Cmax value:

- Subject level baseline is defined as the mean of baseline across periods for each subject. If a period baseline is missing, the mean of available period baselines will be considered as baseline.
- Period level baseline is defined as the difference between the baseline value and subject level baseline for each period and each subject.

5.2.1. Derivations and Handling of Missing Baseline Data

Definition	Reporting Details
Change from baseline in the study	
Change from Baseline	= Post-dose visit value – Baseline value
% Change from Baseline	= $100 \times [(Post-dose visit value – Baseline value) / Baseline value]$
Change from baseline within a period	
Change from Baseline in Period X	= Period X Post-dose value – Period X baseline value

% Change from Baseline in Period X	= $100 \times [(Period\ X\ Post-dose\ value - Period\ X\ baseline\ value) / Period\ X\ baseline\ value]$
------------------------------------	--

NOTES:

- Unless otherwise specified, the baseline definitions specified in Section 5.2 Baseline Definitions (the baseline of the study and the baseline of each period (unadjusted)) will be used for derivations for endpoints / parameters and indicated on summaries. Unless otherwise stated, if baseline data is missing or post-dose data is missing no derivation will be performed and (%) change from baseline will be set to missing.
- The relevant baseline definition will be footnoted on all displays involving change from baseline.

5.3. Other Considerations for Data Analyses and Data Handling Conventions

Other considerations for data analyses and data handling conventions are outlined in the appendices:

Section	Component
10.1	Appendix 1: Protocol Deviation Management and Definitions for Per Protocol Population
10.2	Appendix 2: Schedule of Activities
10.3	Appendix 3: Assessment Windows
10.4	Appendix 4: Study Phases and Treatment Emergent Adverse Events
10.5	Appendix 5: Data Display Standards & Handling Conventions
10.5	Appendix 6: Derived and Transformed Data
10.7	Appendix 7: Reporting Standards for Missing Data
10.8	Appendix 8: Values of Potential Clinical Importance

6. STUDY POPULATION ANALYSES

6.1. Overview of Planned Study Population Analyses

The study population analyses will be based on the “Safety” population, unless otherwise specified.

Study population analyses including analyses of subject’s disposition, protocol deviations, demographic and baseline characteristics, prior and concomitant medications, and exposure and treatment compliance will be based on GSK Core Data Standards. In this document, Appendix 12 contains a list of data displays and analysis sets planned for the informal interim analysis.

Details of the planned displays and analysis sets for final study reporting will be presented in **Error! Reference source not found.**: List of Data Displays.

7. SAFETY ANALYSES

The safety analyses will be based on the “Safety” population, consisting all subjects who had a dose (including those who had partial dose) of study treatment.

7.1. Adverse Events Analyses

Adverse events analyses including the analysis of adverse events (AEs), Serious (SAEs) and common ($\geq 5\%$) AEs by overall frequency will be based on GSK Core Data Standards. The details of the planned displays are provided in **Error! Reference source not found.**: List of Data Displays.

7.2. Adverse Events of Special Interest Analyses

Adverse events of special interest are those considered possibly related to/associated with stomach erosion, adrenal insufficiency and renal impairment.

A comprehensive list of MedDRA terms based on clinical review will be used to identify each type of event. Changes to the MedDRA dictionary may occur between the start of the study and the time of reporting and/or emerging data from on-going studies may highlight additional adverse events of special interest, therefore the list of terms to be used for each event of interest and the specific events of interest will be based on the safety review team (SRT) agreements in place at the time of final reporting. The details of the planned displays are provided in **Error! Reference source not found.**: List of Data Displays.

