### **8.1.3. Renal Withdrawal Criteria**

A participant that meets any of the following bulleted criteria will be withdrawn from the study:

- New onset of any clinically significant and persistent haematuria / proteinuria (Spot Urine Protein Creatinine (UPC) ratio  $>0.5$ ) in the absence of another clinical explanation e.g. calculus / infection. If trace proteins are detected, repeat test should be performed within 24 hours.
- If there is any change in serum creatinine  $> 26 \mu\text{mol/L}$  (0.3 mg/dl) from baseline or  $> 50\%$  from baseline. If change in serum creatinine measures at  $> 26 \mu\text{mol/L}$  (0.3 mg/dl), repeat within 24 hours. If confirmed, the participant will be withdrawn, and further investigations will be performed.
- Persistent hypophosphataemia (less than 0.8mmol/L) confirmed by repeat testing. If a participant meets the withdrawal criteria for hypophosphataemia, then further investigations will be performed.

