### **9.2.3. Follow-up of AEs and SAEs**

After the initial AE/SAE report, the investigator is required to proactively follow each participant at subsequent visits/contacts. All SAEs, and non-serious AEs of special interest (namely stomach erosion, adrenal insufficiency or renal impairment as defined under the stopping and withdrawal criteria above), will be followed until the event is resolved, stabilized, otherwise explained, or the participant is lost to follow-up (as defined in Section 8.3). Further information on follow-up procedures is given in [Appendix 3](#).

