10.6.3. Safety

Adverse Events
[AE'S OF Special Interest]

 • Stomach erosion • Adrenal insufficiency • Renal impairment (Note: Protocol defines renal stopping and withdrawal criteria which are not "renal impairment" in the strict sense)

Laboratory Parameters

 • If a laboratory value which is expected to have a numeric value for summary purposes, has a non-detectable level reported in the database, where the numeric value is missing, but typically a character value starting with '<x' or '>x' (or indicated as less than x or greater than x in the comment field) is present, the number of decimal places in the observed values will be used to determine how much to add or subtract in order to impute the corresponding numeric value. 
 ○ Example 1: 2 Decimal Places = '<x' becomes x - 0.01 ○ Example 2: 1 Decimal Places = '>x' becomes x + 0.1 ○ Example 3: 0 Decimal Places = '<x' becomes x - 1 ○ For values '<=x' or '>=x' the value itself ('x') should be imputed as the numeric value. • Renal biomarker data will be included in the final study analysis. The parameters will be corrected using the following formula, and the units are ng/mg Corrected KIM-1=8.8*Urine KIM-1(pG/mL)/Urine Creatinine (umol/L) Corrected NGAL=8800*Urine NGAL(nG/mL)/Urine Creatinine (umol/L)

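### The SAP identifies adverse events of special interest from an open MedDRA term list, not the protocol's stopping criteria, so a participant meeting a renal or adrenal criterion can be missing from the count

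*SAP*

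**What the plan says.** Protocol 9.2.3 sets out which non-serious AESIs are followed to resolution: "stomach erosion, adrenal insufficiency or renal impairment as defined under the stopping and withdrawal criteria above". The criteria it points to are these:

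- **Renal (Protocol 8.1.3):** a creatinine change above 26 µmol/L or above 50% from baseline; persistent phosphate below 0.8 mmol/L; or new, clinically significant and persistent haematuria/proteinuria (UPC ratio above 0.5) with no other clinical explanation.
- **Adrenal (Protocol 8.1.4, Part B):** early-morning cortisol below 420 nmol/L without a rise above 250 nmol/L after ACTH.
- **Stomach erosion (Protocol 8.1.7):** confirmed clinically with a specialist's opinion, and endoscopy if required.

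SAP 7.2 takes another route: "A comprehensive list of MedDRA terms based on clinical review will be used to identify each type of event". It adds that the list of terms and the specific events of interest "will be based on the safety review team (SRT) agreements in place at the time of final reporting", and refers the reader to the List of Data Displays for the outputs.

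SAP 10.6.3 names the same three events but remarks of the renal one that "Protocol defines renal stopping and withdrawal criteria which are not" renal impairment strictly speaking. It gives no rule for participants who meet those criteria. SAP 2.1 declares only the Ctau change.

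**The concern.** Kidney, stomach and adrenal gland are the three organ risks in the protocol's risk table (3.3.1), and safety is the primary objective. The protocol gives objective renal and adrenal thresholds, and the renal ones feed a rule that stops dosing. Under the SAP, a participant who crosses a threshold enters the AESI count only if an adverse event was recorded and its coded term is on the list.

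The list is also open at a point when treatment codes have been released. SAP 3.1.1.3 keeps the study team blinded until database freeze "except for the unblinded site Pharmacist, unblinded study Pharmacokineticist and SMG Pharma Safety representative", and no step fixes the AESI terms before that freeze. An AESI count whose definition can still move after unblinding is weaker evidence than one fixed in advance.

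**Working it through.** No sample size, power or event-rate figure is at issue. The check compares the two documents and adds one piece of arithmetic on creatinine.

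**1. Can a criterion be met without an adverse event term?** Protocol 10.9.1 makes an abnormal laboratory result an adverse event only when the investigator judges it clinically significant. The creatinine criterion ("If there is any change in serum creatinine" beyond the stated limits, with a rise above 26 µmol/L repeated within 24 hours) and the phosphate criterion ("Persistent hypophosphataemia (less than 0.8mmol/L) confirmed by repeat testing") are numerical. So is the cortisol/ACTH criterion. Each can therefore be met without a recorded adverse event. If one is recorded, its term may or may not be on the final list. Haematuria/proteinuria already requires clinical significance, and stomach erosion a clinical diagnosis, so the gap mainly concerns creatinine, phosphate and symptom-free cortisol/ACTH failures.

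**2. Would the laboratory displays flag such a case?** SAP 10.8.1 gives potential clinical importance (PCI) limits for creatinine as absolute values: high flag above 112 µmol/L in men and above 92 in women; low flag below 66 and below 49. There is no change-from-baseline limit.

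- For baseline b, the smallest whole-number value meeting the protocol criterion is the first integer above min(b + 26, 1.5b).
- Because 1.5b ≥ b + 26 once b ≥ 52, that value is b + 27 for b ≥ 52.
- Men: b + 27 ≤ 112 gives b ≤ 85. Women: b + 27 ≤ 92 gives b ≤ 65.
- Below b = 52 the qualifying value is lower still: at b = 51, 1.5 × 51 = 76.5, so 77.
- Example: a man going from 70 to 97 µmol/L rises by 27 (27/70 = 39%). If confirmed on repeat he meets Protocol 8.1.3, but 97 is below 112, so there is no flag.
- With the low flags added, men with baselines of 66 to 85 and women with baselines of 49 to 65 can meet the criterion with neither value flagged.

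These bounds are for the smallest qualifying rise; larger rises are flagged from lower baselines. Phosphate behaves differently. Any value below 0.8 mmol/L is also below the PCI limit of 0.87, so it is flagged as a laboratory value, though not as an AESI. SAP 10.8.1 gives no limit for UPC ratio or cortisol.

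**3. When is the list fixed?** SAP 3.2 places the final analyses after database freeze and distribution of randomization codes. SAP 7.2 ties the terms and events to agreements at final reporting. By contrast, SAP 4.1 requires protocol deviations to be reviewed before unblinding and freeze. No equivalent step covers AESIs.

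**4. Are the displays there?** By title, Tables 3.1–3.34 cover all, common, drug-related and serious adverse events, then laboratory, liver, ECG and vital signs. Listings 1–80 follow the same pattern. None is an AESI display, and none names cortisol or a renal or adrenal stopping event. Liver stopping events do have their own tables (3.23 and 3.24).

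**5. Size.** Protocol 8.1.2 stops dosing when two or more participants across all parts meet the renal withdrawal criteria. Two of 54 planned participants is 2/54 = 3.7%. Under SAP 7.2 the matching renal AESI count could be 0, 1 or 2, depending on adverse event recording and the term list.

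**The case against.** Several points on the other side carry weight.

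- **Protocol 9.2.3 is a follow-up rule.** It concerns events that are already adverse events, and Protocol 10.5.1 plans no separate AESI analysis. On that view SAP 7.2 adds an analysis rather than replacing one. This weakens any complaint that SAP 2.1 conceals a change. It does not remove the mismatch: 9.2.3 is the protocol's only AESI definition, and SAP 7.2 commits to an AESI analysis.
- **The definitions are not all laboratory-based.** Stomach erosion and haematuria/proteinuria need clinical judgement, and adrenal cases go to an endocrinologist for confirmation. This stands and limits what can be derived from the database alone.
- **The participants would not disappear from the report.** Reasons for withdrawal and discontinuation are in Listings 5–8, all reported adverse events in Listings 28–29, and chemistry changes from baseline in Tables 3.9–3.10. In a study of this size a reported event cannot be hidden by a term list. This also stands; what is at risk is the AESI count.
- **Recording is likely.** Protocol 9.1.5 requires clinically relevant laboratory changes to be entered as adverse events, and a final list could well include terms such as creatinine increased. So the loss is possible rather than expected, but nothing in the SAP prevents it.

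A reader might infer that terms will be chosen with knowledge of treatment. The documents do not say so. They do not give the safety review team's membership, SAP 7.2 explains the timing by MedDRA updates and emerging data, and SAP 3.2 includes a blinded dry run before lock. Lack of a lock is an unguarded risk, not a demonstrated bias.

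**Conclusion.** The point holds. The two documents identify AESIs differently, the SAP notes the renal discrepancy without resolving it, the list has no required lock before unblinding, and the promised displays are not in Appendix 12. A participant who meets the creatinine, phosphate or cortisol/ACTH criterion can be missing from the AESI count. At the extreme, the renal halt rule could be met with no renal AESI counted.

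This assumes that no adverse event was recorded or that its term is off the final list, and that a creatinine rise above 26 µmol/L was confirmed on repeat.

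Three stronger readings are not supported. A single renal event does not halt the study, since Protocol 8.1.2 needs two participants. A symptom-free cortisol/ACTH failure meets 8.1.4 but not the adrenal halt rule, which also needs clinical signs or symptoms. And the lack of a display titled for cortisol does not show that cortisol will go unreported: it is a protocol-required laboratory test and could appear in a general laboratory output.

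**What to change.** 1. Count as a renal or adrenal AESI every participant who meets the protocol's own criteria. Derive creatinine and phosphate (after the required repeat confirmation) and cortisol/ACTH from the database, whether or not an adverse event was reported. Take haematuria/proteinuria and stomach erosion from the investigator's or specialist's recorded determination. Keep the MedDRA terms as a supplementary search.
2. Fix the MedDRA term list and dictionary version before database freeze and unblinding, and label later additions post hoc.
3. Add the AESI table and listing for each part that SAP 7.2 refers to. In Part B include Day -1 and Day 11 cortisol and any ACTH result.

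The cost is SAP wording and a few displays from data already collected. No clinical rule, threshold or assessment changes.
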